#### Recall by Genotype: Neuropeptide Stimulation

#### **BROAD GOALS**

The overall goals of this protocol are to 1) investigate the neuroendocrine control of reproduction, 2) investigate the physiology of kisspeptin administration in the human.

#### I. BACKGROUND & SIGNIFICANCE

# A Shifting Paradigm in Reproductive Endocrinology: Discovery of a GPR54 as a Key Modulator of GnRH Secretion

The hypothalamic hormone GnRH sits atop the reproductive cascade of all mammals as a central driver of pituitary gonadotropin secretion. Its commanding role in this biological hierarchy allows it to control pulsatile gonadotropin secretion, modulate gonadal steroid feedback, and bring about full fertility in the adult. Yet, what turns on GnRH secretion at the time of puberty? And once it is turned on, what sustains the physiological amplitude and frequency so essential for normal reproductive function?

To find modulators of GnRH secretion, we utilized genetic tools in patients with GnRH deficiency (i.e., idiopathic hypogonadotropic hypogonadism [IHH]), a clinical syndrome defined by low sex steroids in the setting of low gonadotropins that results from the failure of a normal pattern of pulsatile GnRH secretion . In 2003, we discovered that, **in both the human and the mouse**, mutations in *GPR54* cause hypogonadotropic hypogonadism which can be corrected by the administration of exogenous GnRH . More recently, we identified an activating mutation in *GPR54* in a girl with central precocious puberty . Taken together, these loss- and gain-of-function mutations demonstrate that the kisspeptin/GPR54 pathway is a genetic determinant and important gatekeeper of pubertal function in the human.

#### **Kisspeptin: the Ligand for GPR54**

The ligand for GPR54 is encoded by the gene *KISS1* . Its full-length gene product, kisspeptin, is a 154-amino-acid protein that is proteolytically processed to a 54-amino-acid peptide, kisspeptin 68-121, initially named metastin based on its ability to inhibit tumor metastasis. Smaller C-terminal fragments of 14, 13, and 10 amino acids can also activate GPR54. The 10-amino-acid (decapeptide) isoform of kisspeptin (kisspeptin 112-121) is the isoform used in this protocol. Although the terms "kisspeptin" and "metastin" can both be found throughout the literature, there have been recent proposals to standardize the nomenclature to "kisspeptin." The term "kisspeptin" will be used throughout this protocol.

# Kisspeptin is a Powerful Stimulator of GnRH-Induced Gonadotropin Release *in vivo* Kisspeptin peptides are the most powerful stimulators of gonadotropin secretion on a molar basis that have ever been studied in mammalian species including rodents,  sheep,  and monkeys. 

- The stimulatory effect of kisspeptin is extraordinarily potent, as intracerebral doses as low as 1 fmol evoke significant LH responses.
- The effects of kisspeptin on LH secretion can be completely abrogated by a GnRH antagonist. 8,15 Thus, kisspeptin acts to stimulate GnRH release, which in turn stimulates LH secretion.
- Kisspeptin is unable to stimulate LH release when given to Gpr54 knockout mice, suggesting that the stimulatory effects of this peptide are mediated only through its cognate receptor. 

- However, kisspeptin is able to stimulate LH release when given to Kiss1 knockout mice, demonstrating its powerful stimulating effects even in the face of abiding hypogonadism.
- Kisspeptin may have a subtle effect on gonadotropin secretion directly at the pituitary.
   This is a controversial point in the literature and the effect is modest at best,
   predominantly limited to synergism with GnRH.
- In hyperprolactinemic mice, which exhibit a form of acquired hypogonadotropism, kisspeptin is able to restore GnRH and LH release. 18

# What does the Discovery of Kisspeptin Mean from a Physiologic Perspective? Probe of the GnRH Neuron

Because kisspeptin is a powerful stimulus for GnRH secretion, administration of kisspeptin offers a method to directly interrogate the function of GnRH neurons in humans, just as GnRH administration has served as a probe of pituitary gonadotrope function in humans for decades. We hypothesize that, in order to respond to kisspeptin with an increase in serum LH, humans must have a certain "threshold" number of GnRH neurons positioned properly within the hypothalamus, adequate GnRH synthetic capacity, and normal secretory mechanisms of GnRH and LH. Thus, in pathophysiologic states that compromise the integrity of the GnRH neurons, the response to kisspeptin would be reduced or attenuated. Therefore, our goal is to use kisspeptin administration as the first direct probe of GnRH neuronal integrity in human reproductive biology to gain new insights into GnRH neuronal function (or dysfunction) in the context of gene variants that impact central regulation of the reproductive axis.

#### **Kisspeptin Administration to Humans:**

The following section 1) lists the various isoforms, doses, and modes of the worldwide experience with administration of kisspeptin in human studies to date, and 2) summarizes key findings from these studies.

Kisspeptin 112-121 (the 10-amino-acid isoform used in this protocol) has been given by our group and others in the following scenarios:

- A) Single Boluses (doses: 0.01 32 nmol/kg; routes: intravenous (IV), subcutaneous (SC))
  - Healthy men
  - Healthy women (including those taking oral contraceptives and with progestin implants)
  - Healthy postmenopausal women
  - Patients with low testosterone and type 2 diabetes mellitus
  - Patients with IHH
- B) Multiple Boluses (doses: 0.24 2.4 nmol/kg IV q1-2 hours for up to 5 boluses)
  - Patients with IHH
- C) Brief Infusions (doses: 0.02-0.72 nmol/kg/hr IV for 30 min followed by 0.01-0.36 nmol/kg/hr IV for 60 min)
  - Healthy cycling women
- C) Long Infusions (doses: 1.1 9.5 nmol/kg/hr IV for 7 24 hours)
  - Healthy cycling women 
  - Healthy men
  - Healthy postmenopausal women

- Patients with low testosterone and type 2 diabetes mellitus
- Patients with IHH
- Women with hyperprolactinemia

In addition, the 54-amino-acid isoform of kisspeptin (kisspeptin 68-121) has also been given in the following scenarios:

- A) Single Boluses (doses: 0.15-12.8 nmol/kg SC)
  - Healthy women (in all phases of the menstrual cycle)
  - Women with hypothalamic amenorrhea
  - Women undergoing ovulation induction
  - Women with or at risk of ovarian hyperstimulation syndrome
- B) Multiple boluses (dose: 6.4 nmol/kg SC for up to 8 weeks)
  - Healthy women
  - Women with hypothalamic amenorrhea
- C) Brief Infusions (doses: 0.0075-2.4 nmol/kg/hr IV for 1.25-3.75 hours)
  - Healthy men
- D) Long Infusions (doses: 0.01 1 nmol/kg IV and SC for up to 10 hours)
  - Healthy cycling women
  - Women with hypothalamic amenorrhea

## **Kisspeptin Safety Data in Humans:**

Kisspeptin has a track record of safety in humans. It has been given to over 150 subjects, both healthy volunteers and patients with reproductive conditions, in studies at 3 centers using 2 different isoforms at a wide range of doses. 19-21,34,36,37,43

Importantly, no serious adverse events related to kisspeptin have occurred in our studies or, to our knowledge, in studies conducted by other investigators. Kisspeptin has been given to women undergoing ovulation induction for *in vitro* fertilization which has resulted in 12 successful pregnancies with no adverse effects Kisspeptin has also been given with no adverse effects to subjects with medical conditions such as type 2 diabetes, hypothyroidism, hypertension, hyperlipidemia, and anxiety/depression, and who were taking prescription medications for these conditions. ([name], unpublished results, [name], personal communication, March 24, 2013, and [name], personal communication, June 15, 2013). Full details are available in the Kisspeptin Investigator Brochure.

#### **Design of the Study**

To assess the physiologic response to the IV administration of the C-terminal decapeptide of human kisspeptin (kisspeptin 112-121), frequent blood sampling (12 h) will be performed to provide detailed neuroendocrine characterization of endogenous LH secretion prior to kisspeptin administration and to evaluate the response after kisspeptin administration.

#### **II. SPECIFIC AIM**

To employ exogenous administration of kisspeptin to directly interrogate human GnRH neurons *in vivo* using GnRH-induced LH secretion as a surrogate marker of adequate GnRH neuronal fate specification, migration, hormone synthesis, secretion, and action.

#### **Hypotheses:**

Patients with a positive but comparatively attenuated response to kisspeptin will have defects in GnRH neuronal fate specification or migration that reduce either the total complement of GnRH neurons or the coordinated activity of the GnRH neuronal population (e.g. mutations in the genes encoding fibroblast factor receptor 1 [FGFR1]).

Individuals ascertained from the MGB Biobank with rare variants in genes that have been linked to reproductive axis function will have attenuated endogenous LH pulse amplitude or pulse frequency.

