#### **III. SUBJECT SELECTION**

The goal of this protocol is to administer kisspeptin to subjects carrying genetic variants of interest and relevant control subjects.

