#### **Enrollment Targets**

Variant-carrying subjects:

 Variant-carrying men and women (n=120: 60 males, 60 females to have 50 males and 50 females complete the study)

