#### **Inclusion Criteria**

#### All subjects will meet the following criteria

#### History:

- genetic variant(s) predicted to be linked to reproductive axis (dys)function
- all medical conditions stable and well controlled
- for men
  - o age 18-60 years
- for women
  - o age 18-40 years
- no condition (medical, mental, or behavioral) that, in the opinion of a study investigator, would likely interfere with participation in/completion of the protocol
- no current or recent use of a medication (including hormonal replacement) that, in the
  opinion of a study investigator, can modulate the reproductive axis or willing to complete
  an appropriate washout for that particular medication and its method of administration no
  active illicit drug use
  - any active use of marijuana will be evaluated by a study medical professional to determine if it may impact study participation; individuals who regularly use marijuana may be asked to washout as referenced in the medication washout section below
- no excessive alcohol consumption (< 10 drinks/week)

- for women
  - not breastfeeding
  - not pregnant
- if applicable, willing to use birth control methods (as approved by a study medical professional) during the entire study

Physical examination:

- normal blood pressure, (systolic BP < 140 mm Hg, diastolic < 90 mm Hg) Laboratory studies:
  - for women
    - negative serum hCG pregnancy test at the time of screening (additional urine pregnancy test will be conducted prior to drug administration)
  - · hemoglobin within sex-specific reference range

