#### STATISTICAL DESIGN AND POWER

Individuals recruited from the Biobank will undergo baseline neuroendocrine LH pulse pattern evaluation, as well as Kisspeptin and GnRH stimulation testing. Boys and girls with delayed puberty have kisspeptin-stimulated GnRH induced LH pulse amplitude 70% lower than healthy men and luteal phase women (144-145, 147). Therefore, we conservatively estimated a 50% reduction in kisspeptin-stimulated GnRH induced LH pulse amplitude in individuals at highest genetic risk compared to those at lowest risk. To detect a 50% decrease in the LH amplitude, 25 participants in each group would be required to provide a statistically meaningful result (80% power, one-sample exact binomial test). Therefore, the study would enroll 25 individuals (males and females combined) in the high risk group and 25 individuals (males and females combined) in the low risk group for a total of 50. To allow for a 15% estimated drop-out rate, 60 participants (males and females combined) will be enrolled.

The hypotheses will be accepted if subjects at high genetic risk demonstrate reduced endogenous and exogenous kisspeptin-induced LH pulse amplitude compared to individuals at low genetic risk.

Since healthy men and women in the luteal phase have similar responses to exogenous kisspeptin (144, 145), an interim analysis is planned to ensure that this remains true in men and luteal phase women in this study. If it is not the case, then the study would enroll 50 individuals (males and females combined) in the high risk group and 50 individuals (males and females combined) in the low risk group for a total of 100. This possibility is accounted for in study recruitment and analysis.

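### The first hypothesis infers the defect from the LH response, but the acceptance rule compares genetic-risk groups not tied to that defect, so the rule could accept the hypothesis when it is false

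*Combined protocol and SAP*

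**What the plan says.** Section II (Hypotheses) contains two hypotheses. The first starts from the response and predicts its cause: "Patients with a positive but comparatively attenuated response to kisspeptin will have defects in GnRH neuronal fate specification or migration". FGFR1 mutation is given as an example. The second starts from genotype: Biobank participants with rare variants "will have attenuated endogenous LH pulse amplitude or pulse frequency".

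Statistical Design and Power gives one decision rule: "The hypotheses will be accepted if subjects at high genetic risk demonstrate reduced endogenous and exogenous kisspeptin-induced LH pulse amplitude", relative to those at low genetic risk. The groups are "25 individuals (males and females combined) in the high risk group and 25 individuals (males and females combined) in the low risk group". The sizing assumption reads: "we conservatively estimated a 50% reduction in kisspeptin-stimulated GnRH induced LH pulse amplitude in individuals at highest genetic risk".

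Sampling is by genotype. Section III sets the goal to "administer kisspeptin to subjects carrying genetic variants of interest and relevant control subjects", and the Inclusion Criteria require of all subjects "genetic variant(s) predicted to be linked to reproductive axis (dys)function". Enrollment Targets gives 120 variant carriers, divided by sex but not by gene or gene class.

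Neither Data Analysis nor Statistical Design and Power gives a cut-off for a positive but attenuated response, a classification by mechanism, or an analysis by gene class. High and low genetic risk are not defined by reference to fate-specification or migration genes.

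**The concern.** A lower average response in a high-risk group is compatible with the first hypothesis but does not test it. The hypothesis concerns which defect lies behind an attenuated response. The rule concerns whether one group responds less than another, whatever the reason. If the rule is applied to both hypotheses, the trial could report a mechanistic conclusion (fewer GnRH neurons, or less coordinated ones, in attenuated responders) on evidence that does not separate it from its alternatives.

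The make-up of the sample adds to this. Because participants are recruited on genotype, the mix of genes among attenuated responders partly reflects whom the investigators chose to recruit.

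**Working it through.** **1. The plan's own figure.** The 25 per group can be neither reproduced nor refuted, because alpha, sidedness and the binomial proportions are not stated. At an assumed alpha of 0.05, a one-sample exact binomial test with n = 25 has 72.7% power for 0.50 v 0.25 and 80.1% (two-sided) for 0.50 v 0.77. The drop-out allowance is 50/(1 − 0.15) = 58.8, rounded up to 59, against 60 stated, which is close enough. What matters here is what the figure sizes: a risk-group difference in LH amplitude, not the defect given the response.

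**2. The statements side by side.**

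| Statement | Starts from | Predicts or compares |
|---|---|---|
| First hypothesis | Positive but attenuated response | Fate-specification or migration defect |
| Second hypothesis | Rare variant | Endogenous LH pulse amplitude or frequency |
| Acceptance rule | Genetic-risk group | Endogenous and kisspeptin-induced LH amplitude |

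The rule and the first hypothesis differ in direction. They also differ in grouping: overall genetic risk is not the named defect class.

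**3. Other routes to a low response in the protocol.**
- Background (physiologic perspective): a response needs enough properly placed GnRH neurons, and also adequate GnRH synthesis and normal GnRH and LH secretion.
- Specific Aim: lists synthesis, secretion and action beside fate specification and migration.
- Background (in vivo stimulation): mice lacking the receptor do not respond to kisspeptin. The opening Background section says GPR54 mutations cause hypogonadotropic hypogonadism, so receptor variants could lower endogenous secretion too.

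A high-risk group containing such carriers could meet the rule without any fate-specification or migration defect.

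**4. A check against the planned effect.** Let mean kisspeptin-induced amplitude in the low-risk group be M. Suppose half the high-risk group has amplitude 0 and half has amplitude M. The high-risk mean is 0.5 × 0 + 0.5 × M = 0.5M, a reduction of 1 − 0.5 = 50%. That equals the planned effect, yet nobody is a positive but attenuated responder.

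**5. Illustration with assumed rates (none is in the documents).** Let a_H and a_L be the proportions attenuated in the high- and low-risk groups, with 25 per group and two-sided alpha 0.05. Let f be the fraction of the high-risk group with a fate-specification or migration variant. Assume that all high-risk variants attenuate equally and that low-risk participants carry no such variant.

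Power = Φ{[(a_H − a_L) − 1.96·√(2p̄(1 − p̄)/25)] / √([a_H(1 − a_H) + a_L(1 − a_L)]/25)}, where p̄ is the average of the two proportions.

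For 0.8 v 0.4: (0.4 − 1.96 × 0.1386)/0.1265 = 1.015, so power is 84.5%.

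Share of attenuated responders in the named class = f·a_H/(a_H + a_L).

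| a_H v a_L | Power | f = 0 | f = 0.25 | f = 0.5 | f = 1 |
|---|---|---|---|---|---|
| 0.8 v 0.4 | 84.5% | 0% | 17% | 33% | 67% |
| 0.7 v 0.3 | 82.8% | 0% | 18% | 35% | 70% |
| 0.6 v 0.2 | 84.5% | 0% | 19% | 38% | 75% |

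Power does not depend on f; the share depends on it entirely. At f = 0 the kisspeptin comparison would be positive 83–85% of the time, although no attenuated responder had the predicted defect. The rule also requires reduced endogenous amplitude, so the chance of full acceptance is at most that.

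**The case against.** The strongest reply is that the first hypothesis is an inverted sentence and not a planned reverse inference. The Background already says that conditions compromising GnRH neurons would reduce the response. The General Outline of Protocol sets out to assess the response in variant carriers, and the title is recall by genotype. This is persuasive about intent and supplies the wording for the fix. It does not rescue the rule, which even on that reading uses overall genetic risk and not the named defect class.

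A second reply is that the plural may not include the first hypothesis. Statistical Design and Power opens with Biobank recruits, whereas the first hypothesis speaks of patients. The plural could refer to the endogenous and kisspeptin-induced limbs of the rule. The section also cites references 144, 145 and 147 although the list ends at 59, so its text may come from another document; that is possible, not proven. The ambiguity stands. It is why the conclusion here is that the rule could, not would, accept the first hypothesis.

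Two stronger readings are tempting. A reader might infer that the protocol offers kisspeptin response as a diagnostic test for genotype and so calculate predictive values. The documents propose no such test, the aim is physiological, and neither accuracy nor prevalence is given. A reader might also infer that the design can never address the first hypothesis. That goes too far: genotype is known and response is measured, so gene class by response can be tabulated within the sample. What is absent is a prespecified analysis. What fails is generalising beyond the recruited mix.

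**Conclusion.** The concern holds as a mismatch between a stated hypothesis and a stated decision rule. The first hypothesis reasons from response to defect; the rule reasons from risk group to response, with no link between risk group and the named defects. Because the protocol describes other causes of a low response, the rule can be met when the first hypothesis is false.

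The size cannot be fixed from the documents. The 50% example needs only the planned effect and an assumed mix of non-responders and normal responders. The range of 0% to 67–75% for the share of attenuated responders in the named class rests on assumed attenuation rates and an unknown f; it illustrates dependence on recruitment and is not an estimate for this trial. The conclusion also assumes that the plural in the acceptance sentence covers the first hypothesis, which is the plain reading but not the only one. The risk-group comparison itself is not undermined by this point.

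**What to change.** - **Reword the first hypothesis** in the genotype-to-response direction: carriers of prespecified fate-specification or migration variants have a positive but lower kisspeptin-induced LH response than low-risk participants. List the genes, and say what counts as a positive response, before the data are examined.
- **Report that contrast as exploratory**, with its confidence interval.
- **State in section II the hypothesis that Statistical Design and Power tests**, namely lower LH pulse amplitude at high than at low genetic risk. Section II does not now contain it.
- **Limit the acceptance sentence to that hypothesis.** The second hypothesis then needs its own criterion or an exploratory label.
- **Add one sentence** saying that a risk-group difference does not show which defect attenuated responders have.

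The cost is some redrafting, a narrower claim, and one exploratory contrast that will be imprecise because no number is set by gene class. No participants or procedures are added.

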#### **III. SUBJECT SELECTION**

The goal of this protocol is to administer kisspeptin to subjects carrying genetic variants of interest and relevant control subjects.

#### **Enrollment Targets**

Variant-carrying subjects:

 Variant-carrying men and women (n=120: 60 males, 60 females to have 50 males and 50 females complete the study)

#### **Inclusion Criteria**

#### All subjects will meet the following criteria

#### History:

- genetic variant(s) predicted to be linked to reproductive axis (dys)function
- all medical conditions stable and well controlled
- for men
  - o age 18-60 years
- for women
  - o age 18-40 years
- no condition (medical, mental, or behavioral) that, in the opinion of a study investigator, would likely interfere with participation in/completion of the protocol
- no current or recent use of a medication (including hormonal replacement) that, in the
  opinion of a study investigator, can modulate the reproductive axis or willing to complete
  an appropriate washout for that particular medication and its method of administration no
  active illicit drug use
  - any active use of marijuana will be evaluated by a study medical professional to determine if it may impact study participation; individuals who regularly use marijuana may be asked to washout as referenced in the medication washout section below
- no excessive alcohol consumption (< 10 drinks/week)

- for women
  - not breastfeeding
  - not pregnant
- if applicable, willing to use birth control methods (as approved by a study medical professional) during the entire study

Physical examination:

- normal blood pressure, (systolic BP < 140 mm Hg, diastolic < 90 mm Hg) Laboratory studies:
  - for women
    - negative serum hCG pregnancy test at the time of screening (additional urine pregnancy test will be conducted prior to drug administration)
  - · hemoglobin within sex-specific reference range

